Overview of approach. We propose a 2-arm randomized trial (RD vs. FTF) using intent-to-treat principles. Both arms will include individual monthly behavioral sessions (participant & caregiver), an eSLD, and increased PA. The RD arm will include group PA (2 session/wk.) delivered using video conferencing and will use commercially available web-based applications for self-monitoring and participant feedback for diet (Lose it!), PA (Fitbit activity tracker), and weight (wireless scales). The FTF arm will include a prescription for self-directed PA, and self-monitoring of diet and PA using paper/pencil self-reports modified for use with adults with IDD. The primary outcome (weight) will be assessed during home visits at baseline (mo. 0), following weight loss (6 mos.), during (12 mos.) and following maintenance (18 mos.) and after 6 mos. of no contact follow-up (24 mos.).

Table 1: Design Overview		INTERVENTION GROUPS
	Remote Delivery	Face-to-Face Delivery (FTF)
Behavioral sessions		
Delivery method	Individual video conferencing (Zoom on the iPad)	Individual FTF home visit
Meeting frequency /session duration		
Weight loss (0-6 mos.)	Monthly/45-60 min.	Monthly/45-60 min.
Maintenance (7-18 mos.)	Monthly/45-60 min	Monthly/45-60 min .
Diet	eSLD (portion controlled entrées and low kcal shakes + SLD)	eSLD (portion controlled entrées and low kcal shakes + SLD)
Supervised MVPA		
Delivery method	Group video conferencing (iPad mini) (10-12 participants)	NA
Session frequency /duration		
Weight loss (0-6 mos.)	2x/wk./30 min	NA
Maintenance (7-18 mos.)	2x/wk./30 min	NA

MVPA (supervised + unsupervised) (0-18 mos.)	150 min/wk.	150 min/wk.
Self-Monitoring (Diet)	Lose it! app	Self-report/pencil/paper
Self-Monitoring (PA)	Fitbit	Self-report/pencil/paper
Self-Monitoring (Weight)	Wireless scales	Portable scale-monthly FTF visit

eSLD=enhanced Stop Light diet; MVPA = Moderate-to-vigorous physical activity, NA = not applicable

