Participant eligibility. *Inclusion criteria:* 1) Age 18 yrs. and older (at least 50% female) with a diagnosis of mild to moderate IDD as determined by a Community Service Provider operating in Kansas under the auspices of a Community Developmental Disability Organization (CDDO). Participants will be judged competent to provide informed consent by their CDDO, or will have a guardian with power of attorney. Participants will not be enrolled without providing assent, regardless of guardian consent. 2) BMI ≥ 25 kg/m² and body weight ≤ 400 lbs. 3) Sufficient functional ability to understand directions, communicate preferences (e.g. foods), wants (e.g. more to eat/drink), and needs (e.g. assistance with food preparation) through spoken language. 4) Living at home with a parent/guardian, or in a supported living environment with a caregiver who assists with food shopping, meal planning, and meal preparation and agrees to serve as a study partner. 5) No plans to relocate outside the study area over the next 24 mos. 6) Internet access in the home. *Exclusion criteria.* 1) Unable to participate in MVPA. 2) Insulin dependent diabetes as this condition requires medical monitoring beyond the scope of this study. 3) Participation in a weight management program involving diet and PA in the past 6 mos. 4) Serious food allergies, consuming special diets (vegetarian, Atkins etc.), aversion to common foods (e.g., unwilling to consume dairy products, vegetables), diagnosis of Prader-Willi Syndrome. 5) Pregnancy during the previous 6 mos., currently lactating or planned pregnancy in the following 24 mos. Participants who become pregnant will be removed from the study and referred to appropriate agencies for consultation. 6) Serious medical risk, e.g., cancer, recent heart attack, stroke, angioplasty as determined by the PCP. 7) Unwilling to be randomized.

Withdrawal/Termination. The subject's participation will be terminated by the investigator if the diet does not appear to be in their best interest or if the subject becomes aggressive towards the study team. To withdraw from the study subject's guardian must contact the PI in writing. Once withdrawal has been received information will no longer be collected from them.

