meal planning, grocery shopping, decisions regarding snack foods, and compliance with the diet in special situations such as eating away from home (restaurants, parties, etc.). Participants will be asked to purchase portion controlled entrées from a list meeting the caloric/fat requirements, as well as F/V, and non-caloric beverages. Recommended PCMs are available at most grocery stores at a cost of \$2.00-\$4.00 each. 2 low-calorie shakes/day will be provided as part of the eSLD only during weight loss (0-6 mos.). Shakes will be shipped to the participant's residence every 2 weeks. eSLD-weight maintenance (7-18 months). During weight maintenance (mos. 7-18), participants will be encouraged to continue using PCMs and will be encouraged to consume 5 one-cup servings of F/V a day. In addition to the PCMs and F/Vs, participants will be counseled to continue to use the SLD to make daily food choices and will receive education on portion control.

Prescribed PA: We will target 150 min/wk. of MVPA (≥ 3 METs) for both the RD and FTF groups as recommended for all adults by the American College of Sports Medicine (61) and the US Department of Health and Human Services (62). Recommended PA will progress from 60 min/wk. (3 d/wk., 20 min./d) to 150 min./wk. (5 d/wk., 30 min./d) at the beginning of mo. 4, and remain at 150 min./wk. through mo. 24. Accumulated PA in bouts ≥ 10 min will be permitted.

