Self-monitoring: All groups will monitor their daily diet and PA behaviors over the course of the 18 mo trial either by traditional pen and paper records or via iPad applications. Additional details regarding self-monitoring are described below.

Self-monitoring-RD group. Diet. Participants will log food/beverages (meals/snacks) using Lose it! by entering the food name and selecting the portion size, or by scanning the bar code of the food item using the iPad. A bar graph displays calories consumed compared with the goal providing immediate feedback (Appendix G). PA. Participants will wear a Fitbit Charge HR (size 35.5 x 28 mm) wireless

activity tracker on their wrist. The Fitbit records time spent in light, moderate or vigorous PA, based on step counts and heart rate (71). Data is automatically transferred to the Lose it! app via Bluetooth connectivity when the device is near the iPad, thus eliminating manual data recording. Lose it! provides immediate feedback on accumulated PA relative to participant goals via a graphic display. We successfully used the Fitbit in our adolescent IDD pilot trial (36). Body weight. Participants will self-weigh during monthly behavioral counseling video sessions using the wireless digital scale provided by the study which automatically syncs with the Lose it! app and updates a visual display of weight change. Reminders. Reminders will be sent via the Lose It! app if no information is reported for a given meal or goal (i.e., PA time). Diet/PA/weight data management. Diet and weight data on the Lose it! app are securely and automatically transferred to the Lose it! for Wellness Professionals web site that is accessible to the health educator. Fitbit data is automatically transferred to cloud storage (Fitabase, San Diego, CA). Diet and PA data will be accessible to health educators for use in behavioral sessions and will be exported to a data base for inclusion in exploratory analyses.

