Self-monitoring-FTF group. Diet/PA. Participants in the FTF group will be provided with a pedometer (Omron HJ-320, Lake Forest, IL) to self-monitor PA. The FTF group will enter diet (entrées, shakes, F/V) and PA data (type, duration, pedometer steps) on paper pictorial tracking sheets designed specifically for adults with IDD. Body weight will be assessed/recorded by the health educator on a calibrated scale during monthly home visits. Diet/PA data management. Diet/PA tracking sheets will be collected by health educators during monthly home visits and will be used as motivation, to inform participant counseling for the FTF group, and entered in a database for inclusion in exploratory analysis.

Incentives. Participants in both groups who complete self-monitoring for diet and PA on 5 of 7 d/wk. will be allowed to choose an iTunes song which will be uploaded weekly to the participant's iPad by study staff. Additionally, participants will receive a \$5.00 gift card for each behavioral session attended, \$20 for completing each of the 5 outcome assessments, and will be allowed to keep the iPad and Fitbit/pedometer on study completion (18 mos.). Study partners will receive gift cards (\$50.00) at 6, 12, and 18 mos. to compensate for the additional burden associated with participation in this trial.

Cost to Participants. All study cost will be paid for by the study including the iPad, fitbit, and exercise equipment. Participants and their families will not be charged if the participant loses any of the equipment, but must return them at the end of the study.

Intervention Deviations: As this study is intent-to-treat, all participants will be encouraged to follow the intervention described above, however they may choose not to follow the prescribed diet, track diet /PA, attend meetings, or weigh themselves. If a participant chooses not to follow the intervention as described, it will be recorded as process data and will not be considered an intervention deviation.

Assessments

Table 2: Assessment schedule					
Study Month	0	6	12	18	24
Outcomes: Primary/Secondary					
Weight/height/WC	X	X	X	X	X
Quality of life	X	X	X	X	X
Cost Analysis	→				

Demographics/health history	X			X	X
Outcomes: Exploratory					
Compliance-Diet/PA	X	X	X	X	
Behavioral session attendance					→
Self-Monitoring-Diet/PA					→
Study partner self-efficacy	X	X	X	X	
Medications	X	X	X	X	X

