Analysis plan. Primary aim. We will construct a two-sided 95% confidence interval for the difference in mean 6 mo. weight loss between the RD and FTF groups. If the lower limit of the confidence interval is >-3 and the upper limit is > 0 we can conclude that RD is non-inferior to FTF. If we find that 6 mo.

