
Missing data. Analysis of our primary aim will be based on intent-to-treat principles using imputation for missing data. If the proportion of participants lost to follow-up differs by treatment we will determine if there are differences in demographic characteristics (sex, age, baseline weight, $p < 0.05$) between completers and those lost to follow-up. If missing data are related to treatment and/or demographic characteristics, we will use model based multiple imputation; otherwise, we will use traditional multiple imputation ($k=5$). Statistical procedures will be performed using SAS version 9.4 or higher.

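### Investigator termination on diet grounds ends study participation with no provision for later weighing, which adds avoidable missing 6-month weights to the primary comparison

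*Combined protocol and SAP*

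**What the plan says.** Under Withdrawal/Termination, the investigator's decision applies to the whole of participation: "The subject's participation will be terminated by the investigator if the diet does not appear to be in their best interest". Aggression towards staff is the other ground. The same paragraph then deals with withdrawal notified in writing by the guardian and adds: "Once withdrawal has been received information will no longer be collected from them". That data stop is written for withdrawal. There is no matching rule, either way, for termination by the investigator.

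Intervention Deviations treats people who stop by their own choice differently: "If a participant chooses not to follow the intervention as described, it will be recorded as process data", and this is not counted as a deviation.

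For the primary aim, the Analysis plan states: "We will construct a two-sided 95% confidence interval for the difference in mean 6 mo. weight loss between the RD and FTF groups". The Missing data section adds: "Analysis of our primary aim will be based on intent-to-treat principles using imputation for missing data". The characteristics it compares between completers and those lost are sex, age and baseline weight. The Primary aim sets the non-inferiority margin at -3 kg.

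**The concern.** An intent-to-treat comparison needs the 6-month weight of everyone randomised, whether or not they are still on the diet. The plan accepts this for participants who choose to stop. It makes no such provision for participants whom the investigator takes off the same diet, although they have not withdrawn consent. No design reason for the difference is given. Weighing people who are off the intervention is already part of the design, since the month 24 visit follows six months without contact.

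Imputation keeps these people in the analysis but does not recover their weights. A judgement that the diet is unsuitable may follow poor response, a medical problem or excessive loss, and each implies a different 6-month weight. The imputation text names neither the reason for stopping nor the monthly weights as predictors. The decision is discretionary. Outcome assessors are blinded, but the document does not say that the investigator who terminates is. Balance between arms is therefore likely, since both use the same diet, but not assured. If terminations were more common in the remote arm and the people stopped had done badly, imputing them near their arm mean would favour non-inferiority.

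There is also a secondary consequence. Secondary aim 2 counts any missing weight as not reaching 5% loss. A participant stopped for losing too much, and not weighed again, would count as a failure at every later visit.

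**Working it through.** The plan states no figure on this point to reproduce. It gives no sample size, standard deviation, dropout rate or termination rate. What follows is an illustration on stated assumptions.

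**Inputs**
- Margin: 3 kg (Primary aim).
- Expected 6-month loss on this diet: 7.0% (prior trial, Aims and Hypothesis).
- Baseline weight: assumed 90 to 110 kg.
- Imputed loss L, taken as the arm mean (assumed): 0.07 × 90 = 6.3 kg to 0.07 × 110 = 7.7 kg.
- p: assumed proportion terminated before month 6 (R remote, F face-to-face).
- T: their actual 6-month loss (assumed).

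**Formula**

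Shift in the remote minus face-to-face difference, imputed minus everyone weighed:

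shift = pR × (LR − T) − pF × (LF − T)

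A positive value favours remote delivery.

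**Results**

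| Terminated before month 6, remote vs face-to-face | Outcome in those stopped | Shift (kg) |
|---|---|---|
| Equal rates, no true arm difference | any | 0 |
| 5% vs 2% | 3 kg worse than imputed | 0.03 × 3 = +0.09 |
| 5% vs 2% | 3 kg better than imputed | 0.03 × (−3) = −0.09 |
| 5% vs 2% | no loss (pessimistic) | 0.03 × 6.3 to 7.7 = +0.19 to +0.23 |
| 10% vs 5% | no loss (pessimistic) | 0.05 × 6.3 to 7.7 = +0.32 to +0.39 |

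Swapping the arms reverses each sign.

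**Timing.** The diet runs for 18 months, and only terminations before month 6 touch the primary outcome. If 5% vs 2% is the total over 18 months, spread evenly, one third falls before month 6. The imbalance is then 0.03 × 6/18 = 0.01, and with no loss the shift is 0.01 × 6.3 to 7.7 = 0.06 to 0.08 kg, or 2 to 3% of the margin.

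**More extreme cases.** With terminations in one arm only and a 3 to 7 kg imputation error, 5% vs 0% gives 0.15 to 0.35 kg (5 to 12% of the margin). 10% vs 0% gives 0.30 to 0.70 kg (10 to 23%).

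**Break-even.** With no loss in those stopped, using up the margin needs an imbalance of 3/7.7 = 39 to 3/6.3 = 48 percentage points before month 6.

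**Precision.** For a design assumed to have 90% power against the 3 kg margin at one-sided 0.025 (SD assumed 5 to 7 kg), losing 2%, 5% or 10% of weights in both arms leaves power of about 90%, 89% or 87%.

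**The case against.** The strongest reply is that this rests on silence and has no demonstrated effect. The explicit data stop applies to guardian withdrawal only, and the visits are scheduled under intent-to-treat, so weighing after termination is open to the team. The event is probably uncommon: the eligibility criteria already exclude insulin-dependent diabetes, serious food allergies, special diets and serious medical risk, physician clearance is requested, and non-adherence does not lead to termination. The upper figures need high, unequal rates and no weight loss in those stopped. The arm-mean assumption is also simpler than the plan's rule, which moves to model-based multiple imputation when missingness is related to treatment or demographics. Monthly weights exist before termination, too; in the remote arm, for example, "Participants will self-weigh during monthly behavioral counseling video sessions".

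Most of this stands as a limit on size, and none of it supplies the missing weights. A team that follows the sentence as written would have no reason to make the month 6 visit. The imputation rule does not name the reason for stopping, and the plan does not say that the monthly weights will be used.

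A second reply is that off-intervention weights can pull the arms together. If remote delivery were truly 3 kg worse among those continuing, and 5% of each arm stopped with equal outcomes, including them would move the difference from −3.00 to 0.95 × (−3) = −2.85 kg. That is correct, but it is the effect an intent-to-treat comparison sets out to estimate.

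A third reply concerns cost. The COVID-19 section delivers assessment materials to homes and moves face-to-face meetings to phone, and a consent change might need renewed consent and assent. These are practical limits, and they do not defeat the change. Removal for pregnancy has the same gap and lies outside this point.

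**Conclusion.** The point holds. As written, termination on diet grounds ends participation, and no section provides for a later weight. Terminations before month 6 therefore add avoidable imputation to the primary comparison. Later ones affect only the secondary and exploratory analyses.

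The likely size is about 0 to 0.4 kg in either direction against the 3 kg margin, and probably near zero because both arms receive the same diet. A one-sided 10% vs 0% split with a 7 kg imputation error would reach 0.70 kg, still well inside the margin. All of this depends on assumed termination rates, an assumed baseline weight of 90 to 110 kg and, for the 0 to 0.4 kg range, imputation at the arm mean. Using the pre-termination monthly weights would reduce it further. The primary conclusion is not at risk. The change is worth making because it costs little and the weights cannot be recovered afterwards. Confidence is medium, since the document is silent rather than explicit on follow-up after termination.

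**What to change.** Reword the termination sentence so that the investigator stops the intervention, not participation in the study. Offer the remaining scheduled weighings at 6, 12, 18 and 24 months unless consent or assent for data is withdrawn, a medical reason makes the visit unsuitable, or staff safety prevents it. Record the date and reason for stopping by arm, and use the observed weights in the primary analysis.

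The cost is one protocol sentence, plus the consent form if it carries the same wording (it is not in the text supplied); that could mean renewed consent and assent for people already enrolled. A few assessments already on the schedule would go to people no longer on the intervention, each between 7 and 10 a.m. after a 12-hour fast, and subject to the pandemic arrangements while those apply. For this reason the weighing should be offered and not required.

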Premise/summary of significance/impact. The premise of this trial is that adults with IDD represent an underserved segment of the US population with a high prevalence of obesity, obesity related chronic disease, and limited options for weight management. On-site group sessions, widely used to deliver weight management in typically developed adults, may be inappropriate for this group who have diverse cognitive, communication and social skills, and who depend on a caregiver for transportation to meeting sites/exercise facilities, and for assistance with meal planning, food shopping and meal preparation. We have demonstrated clinically meaningful 6 mo. weight loss (-7%; 63% \geq 5%) with minimal weight regain at 18 mos. (-6.7%; 57% \geq 5%) with a multicomponent intervention that included an energy reduced diet (eSLD), PA, and behavioral sessions delivered to participants/caregiver during monthly FTF home-visits. Although effective, the logistical burdens and costs associated with individual FTF home-visits, greatly limits the potential reach, scaling and implementation of this approach by agencies serving adults with IDD. Thus, alternative strategies for the delivery of weight management to increase accessibility, reduce costs, and potentially improve outcomes for adults with IDD are warranted. Therefore, the primary aim of this trial is to determine whether a multicomponent weight management intervention delivered remotely (RD) to adults with IDD using video conferencing (Zoom software) on a tablet computer (iPad mini) is non-inferior to weight management delivered FTF. Both intervention arms will include individual monthly at-home behavioral sessions (participant & caregiver), delivered either FTF or video conferencing, an eSLD, and increased PA. The RD arm will include group PA sessions (2 session/wk.) delivered using video conferencing and will use commercially available web-based applications for self-monitoring/participant feedback for diet (Lose it!), PA (Fitbit activity tracker), and weight (wireless scales). As required in a non-inferiority trial, the FTF arm will be identical to the intervention shown to be effective in our previous trial (DK83539) and will include a prescription for self-directed PA, self-monitoring of diet/PA using paper/pencil logs, and weight assessed during home visits.

PRELIMINARY STUDIES

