Cost Analysis. Our previous trial comparing FTF and RD (group phone) for weight management (38) suggests higher costs in the FTF group due to costs for both travel and time associated with home visits. We will conduct a cost effectiveness analysis using between group differences in mean weight loss at 6 and 18 mos. (76). The cost perspective for all analyses will be societal. We will collect data on both program (health educator time, supplies, iPads) and participant/study partner costs (time), prospectively. Time is a component of intervention cost, as time devoted to an intervention cannot be used for work or leisure (77). Participant and study partner time will be valued at the local median hourly wage. These costs, which may be half of the total costs (78, 79), will be gathered via survey (80). We will conduct sensitivity analyses that vary the value of participant/study partner time from \$0.00 to the median hourly wage. The gold standard for measuring cost is a time study, based on a validated flowchart (81, 82). We will validate flowcharts for both study arms and use time studies to measure health educator time and program records to measure cost of supplies. Weight management programs have effects in addition to weight loss (e.g., increased vitality or enhanced attractiveness), thus the value of a program to clients may be imperfectly measured by objective outcomes (weight). Contingent valuation, in which participant's express preferences for programs, will be used to examine the perceived worth of the RD and FTF formats at 6 and 18 mos. (83). If the preference questions have acceptable psychometric properties conditional logistic regressions, with adjustments for clustering by health educator, will be used to analyze how differences in client attributes, anticipated costs/gains affect preferences for delivery formats.

COVID 19: During the Covid-19 pandemic restrictions all assessment materials will be delivered to participant homes. All materials will be disinfected beforehand and will be delivered to participant's homes. A stamped, self-addressed envelope will be included to allow participants to mail surveys and accelerometers back. All face-to-face meetings will be conducted by phone.

Statistical Methods

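### The COVID-19 provision moves the face-to-face comparator to phone, and the analysis plan has no supportive analysis against home-visit FTF

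*Combined protocol and SAP*

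**What the plan says.** The section on premise and significance sets the standard for the comparator: "As required in a non-inferiority trial, the FTF arm will be identical to the intervention shown to be effective in our previous trial". The aims section also describes FTF as identical to the intervention in the earlier trial.

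Under Self-monitoring-FTF group, two components depend on the monthly home visit. Weighing: "Body weight will be assessed/recorded by the health educator on a calibrated scale during monthly home visits". Collection of self-monitoring records: "Diet/PA tracking sheets will be collected by health educators during monthly home visits and will be used as motivation".

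The COVID 19 paragraph then states, for the period of restrictions, "All face-to-face meetings will be conducted by phone". Assessment materials are delivered to homes. The return route covers only two items: "A stamped, self-addressed envelope will be included to allow participants to mail surveys and accelerometers back". No substitute is given for educator weighing or for collecting tracking sheets.

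RD runs by video. On weight, Self-monitoring-RD group says "Participants will self-weigh during monthly behavioral counseling video sessions using the wireless digital scale provided by the study". The COVID 19 paragraph does not mention RD.

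For the primary aim, the Analysis plan builds a two-sided 95% confidence interval for the RD minus FTF difference in 6-month weight loss. Its rule is that if "the lower limit of the confidence interval is >-3 and the upper limit is > 0 we can conclude that RD is non-inferior". Under Missing data, "Analysis of our primary aim will be based on intent-to-treat principles using imputation for missing data". The statistical section names no COVID-19 period, pre-restriction set or other supportive set for this aim.

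**The concern.** A weaker comparator makes non-inferiority easier to show. FTF is defined throughout as home visits, and RD is meant to replace home visits. If part of the FTF arm was counselled by phone in months 0-6 and lost less weight as a result, the pooled difference moves in RD's favour. The rule could then declare RD non-inferior to FTF although RD is worse than home visits by the full margin. Intent-to-treat does not guard against this, because it compares the arms as they were delivered. Nothing planned for the primary aim would show a reader whether it had happened.

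**Working it through.** The documents state no sample size, SD, power or enrolment dates, so there is no planned figure to reproduce. The check sets the texts side by side and then illustrates the size on labelled assumptions.

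**1. What changes in each arm.**

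| Component | FTF under restrictions | RD under restrictions |
|---|---|---|
| Monthly session | Home visit becomes phone | Video, not altered by the text (inference) |
| Review of diet, PA and weight data | Not cancelled (Meeting schedule) | Not cancelled |
| Monthly weighing | Educator weighing has no stated substitute | Self-weighing on the study's wireless scale |
| Tracking records | Collection has no stated substitute | Automatic transfer from the app |
| Orientation home visits | Would also change | Would also change |

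**2. Assumed SD.** In the earlier trial (Background), the eSLD arm lost a mean of 7.0%, and 62.7% of participants reached 5%. Assuming normality, SD = (7.0 - 5)/z(0.627) = 6.17%. Mean BMI was 36.9. With assumed heights of 1.55-1.70 m, mean weight is 88.7-106.6 kg, so the SD is 5.5-6.6 kg. I use 5.5 and 6.5 kg.

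**3. Standard error.** SE = SD × √(2/n), with n per arm assumed to be 50 or 75:
- SD 5.5: 1.100 (n = 50) and 0.898 (n = 75)
- SD 6.5: 1.300 (n = 50) and 1.061 (n = 75)

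**4. Pass rule.** The interval passes if the estimate exceeds both -3 + 1.96 SE and -1.96 SE. The first is the stricter whenever SE > 3/3.92 = 0.765 kg, which holds in all four cases.

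**5. Shift.** Let e be the average share of the FTF arm's months 0-6 spent under phone delivery, and d the weight loss given up under full phone delivery. If the loss is proportional to exposure, the observed difference moves by s = e × d towards RD. Neither e nor d is in the documents. With d = 1.5 kg, e of 10%, 20% and 40% gives s = 0.15, 0.3 and 0.6 kg.

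**6. False-pass rate** when RD is truly 3 kg worse than home-visit FTF: Φ(s/SE - 1.96).

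| s (kg) | SD 5.5, n 50 | SD 5.5, n 75 | SD 6.5, n 50 | SD 6.5, n 75 |
|---|---|---|---|---|
| 0 | 0.025 | 0.025 | 0.025 | 0.025 |
| 0.15 | 0.034 | 0.036 | 0.033 | 0.034 |
| 0.3 | 0.046 | 0.052 | 0.042 | 0.047 |
| 0.6 | 0.079 | 0.098 | 0.067 | 0.082 |

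**7. Precision of a pre-restriction analysis.** If a share g of each arm is excluded, SE grows by 1/√(1 - g), a factor of 1.12 at g = 20% and 1.29 at g = 40%. If the arms truly lose the same, the chance that the interval clears -3 kg is Φ(3/SE - 1.96): 64-92% in the full sample, 54-85% at g = 20% and 43-74% at g = 40%. At a true -3 kg it is 2.5% for any e and d, because no phone-period data from months 0-6 enter.

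**The case against.** The strongest reply is that exposure of the primary endpoint is not shown. The endpoint covers only months 0-6 of a 24-month trial. The document was last updated on 3/20/2020, and no enrolment dates are given. The overlap could be nil. That stands, and it is why the size is left open.

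Next, phone may be as good as home visits. Preliminary Studies reports equivalence of phone and face-to-face group sessions in 295 overweight or obese adults. That sample is not described as having IDD, and the sessions were group rather than individual. The Background says that the effectiveness of alternative delivery in adults with IDD is unknown. Equivalence is possible but cannot be assumed.

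A reader might infer that weighing and self-monitoring simply stop in the FTF arm. The text does not support that. Meeting schedule has educators review diet, PA and weight data at every session in both arms, and the COVID 19 paragraph changes the mode of the meeting without cancelling its content. Sheets filled in at home can be discussed by phone. The diet, shipped shakes, study partner and PA target do not depend on visits either. Only educator weighing and physical collection lack a substitute.

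A reader might also reach for much larger error rates. A 1.2 kg shift would give 15-27%, but it needs, for example, e = 40% with d = 3 kg. The earlier trial's whole 6-month contrast between diets was 7.0 - 3.8 = 3.2 points, or 2.8-3.4 kg on the weights above. A phone effect that large with the diet unchanged is hard to credit. Participants only partly exposed also count for less: if 40% are touched and the overlap is spread evenly, e is about 20%.

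Finally, intent-to-treat on care as delivered is a stated and legitimate choice. The point does not dispute it.

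**Conclusion.** The point holds in limited form, as a cheap improvement. The protocol requires a constant comparator, then alters its delivery for a period, and the statistical section has nothing that speaks to the change. Bias towards non-inferiority to home-visit FTF needs two things: some overlap of months 0-6 with the restrictions, and phone being less effective than home visits. The documents establish neither. For shifts of 0.15-0.6 kg, the false-pass rate would be about 3-10% instead of 2.5%, given the assumed SD and arm sizes; with no overlap or no phone effect it stays at 2.5%. That RD carries on unchanged is inferred from silence, and so is the pooling, since no sentence sets these participants apart. The documents do not support a conclusion that the primary result is biased or that the pooled test is invalid.

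**What to change.** Keep the pooled intent-to-treat interval and the -3 kg rule as the primary test. Before data lock, add to the Analysis plan:

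1. A supportive analysis giving the same interval, read against -3 kg, in all randomised participants of both arms whose month-6 due date fell before FTF visits stopped. One calendar date applied to both arms keeps the comparison randomised. It also leaves out 6-month weights due under the COVID 19 paragraph, which states no weighing method.
2. A report of the share of month 0-6 FTF sessions held by phone, identified by session date. Behavioral lesson content already puts the date in each recording's file name, so no new data field is needed.
3. A wording rule: if the supportive estimate is materially less favourable to RD, the conclusion reads non-inferior to FTF as delivered (home visit or phone). What counts as material should be written down at the same time.

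The cost is one extra, less precise analysis. It also leaves out anyone treated by home visit after visits resumed. It should not be a second required test: with 40% excluded and phone harmless, both tests would pass only 40-72% of the time when the arms truly lose the same. If no month 0-6 window overlaps the restrictions, the two analyses coincide.
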